
Treatment Factors will be assessed by three measures. The Pre-Program Questionnaire (PPQ)⁸¹ is an adaptation of Borkovec and Nau’s format⁸² and is a frequently used measure of treatment credibility. The questionnaire asks subjects to rate how confident they are in the program, how logical the program seems,

how successful they think it will be, how helpful the program leaders will be, and whether they would recommend the program to a friend, on a 10-point Likert-type scale. Treatment Satisfaction will be measured by the Client Satisfaction Questionnaire (CSQ-8), an 8-item scale that uses a 4-point likert scale to indicate participants' appraisal of their satisfaction with the intervention.⁸³ The CSQ-8 has excellent internal consistency, with a coefficient alpha of .87-.93, and evidence for the construct and concurrent validity of this measure has been reported as well.⁸⁴ A one-hour Program Evaluation Focus Group will be conducted with 15 randomly selected HYP participants to gather detailed information about participants' experience of the intervention to guide improvement of its structure and content. These participants will receive \$15 for completing the interview. [name], a sociologist experienced in qualitative methods, will train a member of the study staff to conduct the interviews, which will be audio recorded and transcribed. [name] will explore the data in order to understand participants' perceptions of the program, particularly in relation to PTSD, using Grounded Theory, an emergent constant comparative method.⁸⁹ The secondary analysis (Situational Analysis), will map all major features of participants' characteristics, perceptions, material elements and settings, in order to understand the relations and differences among them. All other participants will complete a brief program evaluation questionnaire with open-ended questions to ascertain likes and dislikes as well as suggestions for improvement of HYP or WLP. Treatment Engagement will be assessed by examining totals of treatment sessions attended and home practice completed.

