Study questionnaires, rating scales, and other assessments will be completed by study participants through an on-line survey or paper questionnaires (when the participant is unable to use the on-line survey and to capture home practice), assisted if needed by trained study staff blinded to condition. When on-line surveys are used to capture data, participants will be provided with a survey link and a code which will allow them to access the survey. The survey link will be sent to the participant in an email from Outlook on the VA network. The access code will be provided to the participant separately by another method, such as a hard-copy presented in-person, verbally over the phone, or a STREEM text. Data will be entered from paper self-report questionnaires or interviews conducted by trained study staff (e.g. CAPS). Within the REDCap database, algorithms will be created to check for inappropriate or missed data entry. Computer algorithms will automatically score questionnaires within the same database. These data will be backed up daily onto a password protected, secured server at the IU School of Medicine. Participant social security numbers, names, addresses and other personally identifiable information will be restricted to authorized personnel to protect confidentiality and will be stored in a separate password protected Microsoft Access Database on the RVAMC secured server. We have experience in setting up data integrity protocols and data back-up to minimize the risk for lost or inaccurate data. Participant personally identifiable information will be restricted to authorized personnel to protect confidentiality. We have experience using this strategy successfully in previous research, accurately completing assessments, protecting patient privacy and minimizing the risk for lost or inaccurate data. For our current PTSD study, audits revealed very low rates of data entry error (0.00079 or 0.079%) and missing data (average of 0.00083 or 0.083%). We have used similar length or longer batteries of measures in several previous or current trials without over-burdening patients. Self-report assessments will be completed via on-line surveys (REDCap) and interviews will be conducted in-person as we have found that rapport is more easily established face-to-face. If multiple attempts have failed for on-line surveys and/or in-person interviews, we have employed two strategies to capture outcome assessments: (1) conduct assessments by phone; and (2) mail questionnaires with postage paid, self-addressed envelope to our office. At times in past studies, participants have needed assistance to cover the cost of driving to the RVAMC for an assessment, especially if they live more than 30 minutes away. In these situations, the Project Coordinator may authorize a \$10 gas card to defray the round trip cost of travelling to a scheduled study visit for assessment purposes. We have previously arranged taxi cab rides to and from our VA. To maintain participant confidentiality, our study staff will adhere to careful interview and data collection procedures. First, participants will be told that their responses will remain confidential and that every effort will be made to fulfill that assurance. Second, the interviews will be conducted in an appropriate setting (i.e., private interview room). Third, any completed paper surveys will be stored in a secure location in our locked RVAMC office in a locked file cabinet. The screening and assessment interviews and study databases (using Microsoft Access) will be designed by trained study staff under the direction of [name] or the Project Manager.

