
Once baseline assessments are completed, the participant will be randomly assigned to the Holistic Yoga Program (HYP) or Wellness Lifestyle Program (WLP). The Holistic Yoga Program (HYP) arm will involve a standardized 16-week, yoga intervention consisting of: 1) a program orientation session conducted by a yoga instructor; 2) once weekly in-person group yoga class (postures, breathing practices, deep muscle contraction practices, relaxation practices) taught by a yoga instructor registered with Yoga Alliance at a minimum of the 200 hour level; 3) audio recordings of guided yoga postures, breathing, and relaxation practices for home-use; 3) a handbook to reinforce concepts taught during in-person session. Patients randomized to the Wellness Lifestyle Program (WLP) arm will participate in a standardized 16-week intervention that will consist of: 1) a program orientation conducted by a trained member of the study staff; 2) once weekly in-person group wellness classes (didactics and discussion of wellness topics and low intensity physical activity consisting of walking taught by a clinical psychologist with experience in trauma with consultation available from an experienced athletic trainer; 3) a handbook to reinforce wellness concepts and physical activity instructions taught during in-person session and to assist with home practice. After completing the program, participants will be asked to complete the same assessments as baseline with the addition of 2 program evaluation questionnaires. To minimize the potential for ascertainment bias, follow-up assessments (8 weeks, 4 months, 7 months) will be conducted by on-line survey and the interviews by a trained research assistant who will be blinded to treatment assignment. Participants will receive \$25 for completing the 8-week assessments, \$35 for completing the 16-week assessments and \$45 for completing the 7-month follow-up assessment. Those who fail screening will be given \$15.

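### The plan does not keep the arm-revealing program evaluation and home-practice records away from the blinded CAPS rater

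*Combined protocol and SAP*

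**What the plan says.** All of these points are in section 5.0 unless noted.

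- **Who rates.** Follow-up self-report is by online survey, and the "interviews by a trained research assistant who will be blinded to treatment assignment". Section 4.0 also says that the outcome assessor is blinded. It limits access to the randomization function to the project coordinator and two other named people, none of whom assess outcomes.
- **Who helps with forms.** Questionnaires are completed online, or on paper if the participant cannot use the survey. Paper is also used to capture home practice. The participant is "assisted if needed by trained study staff blinded to condition". No form is exempted.
- **Default and fallback.** "Self-report assessments will be completed via on-line surveys (REDCap) and interviews will be conducted in-person". If repeated attempts fail, the strategies described are "1) conduct assessments by phone; and (2) mail questionnaires with postage paid".
- **What is added after the program.** The baseline assessments are repeated "with the addition of 2 program evaluation questionnaires". For everyone outside the focus group, one of these forms has "open-ended questions to ascertain likes and dislikes as well as suggestions for improvement of HYP or WLP".
- **Focus group.** Fifteen randomly selected participants from the Holistic Yoga Program (HYP) attend. A sociologist "will train a member of the study staff to conduct the interviews". No date is given, and no staff member is excluded from the role.

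**The concern.** Participants know their arm, so a blinded CAPS interviewer is the plan's stated safeguard against ascertainment bias in the clinician-rated outcome. The other primary measure, the PCL, is self-reported and has no rater to blind. The sample size is based on the CAPS at 4 months.

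The assistance clause gives help with every questionnaire to staff who must remain blind. At the primary visit, one of those questionnaires asks what the participant thought of the program. An answer about postures, breathing practices or walking classes tells the helper which arm it was. A home-practice record would do the same. If the helper is also the CAPS rater, blinding is lost for that participant. It cannot be regained for the 7-month CAPS, which is the test of sustained effect.

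**Working it through.** No effect size or error rate can be recalculated here. The check places the forms in the schedule and then follows who may handle them.

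**1. Are the evaluation form and the primary CAPS in the same battery?** The outcome schedule in section 5.0 states totals of 61 minutes at 8 weeks, 106 at 7 months and 117 at 4 months.

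- Row times repeated at every follow-up: 3 + 6 + 2 + 3 + 7 + 5 + 3 + 6 + 10 + 3 + 3 + 2 + 3 = 56 minutes.
- Adding the CAPS (45): 101 minutes.
- Adding the satisfaction form, CSQ-8 (3), and the program evaluation (8): 112 minutes.

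Each sum is 5 minutes below the stated total (61, 106, 117), so the same small amount is unlisted at all three visits. The differences are unaffected:

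- 106 − 61 = 45, which is the CAPS.
- 117 − 106 = 11 = 3 + 8, which is the CSQ-8 plus the program evaluation.

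Both added forms therefore belong to the 4-month battery, together with the CAPS. This agrees with the text that adds two evaluation questionnaires after the program.

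**2. Would the answers reveal the arm?** The evaluation form is not reproduced. Its stated purpose is to obtain "likes and dislikes as well as suggestions for improvement of HYP or WLP", where WLP is the Wellness Lifestyle Program. Open-ended answers to that would ordinarily mention yoga or the walking and wellness classes. Home practice is guided yoga in one arm and is supported by physical-activity instructions in the other, so a record of what was practised would also identify the arm. This assumes that the record notes the activity.

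**3. Who may see those answers?**

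| Mode | Who handles the form | Exposure of blinded staff |
|---|---|---|
| Online, unaided (default) | Participant | None by this route |
| Online or paper, aided | Blinded staff | Yes |
| Phone | Caller not specified | Possible |
| Mail | Returned to the study office; recipient not specified | Possible at receipt or data entry |
| Paper home-practice record | Same assistance clause | Possible |

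**4. Is the helper kept apart from the rater?** Section 5.0 uses the same general staff term for those who help with questionnaires and for those who conduct the CAPS, and elsewhere calls the interviewer a research assistant. It does not say that they are the same person or that they are different people.

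**5. Does order protect the rating?** No order within a visit is given. If the CAPS came first, the evaluation form could not affect the 4-month rating. It could still affect the 7-month rating if the same person did both. Home-practice records seen before the 4-month visit would not be covered by order at all.

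**6. Are there other safeguards?** The plan has no instruction to participants not to disclose their program and no log of unblinding. It also does not say that the focus group, which only HYP participants attend, is run by someone other than the CAPS rater.

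**7. Is the sample size affected?** No. It reproduces: 60 × 1.35 = 81 per arm, and 162 / 0.70 = 231.4, rounded up to 232.

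**The case against.** The strongest reply is that the plan is already protective and this is only a narrow silence. Self-report is online by default, only the interviews go to the blinded research assistant, and those who can see the randomization do not assess outcomes. Help is given only if needed. Using the CAPS rater for a yoga-only focus group would breach the plan's own blinding statements.

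Much of this stands, and it limits the point to assisted, paper or phone cases. It does not remove it, because in those cases following the assistance clause as written gives revealing forms to people whom the plan needs kept blind.

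A reader might infer more than the documents support:

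- *That the CAPS rater will be unblinded.* The documents leave open whether helper and rater are the same person.
- *That the evaluation form itself names the program.* The form is not shown; the naming is in the plan's description of its purpose. The answers are the source of disclosure.
- *That the CSQ-8 also reveals the arm.* It is described as a rated satisfaction scale, and nothing shows that it does.
- *That rater blinding is the sole defence against expectation bias.* Section 8.0 measures treatment expectations at baseline and accounts for them, and the comparator is an attention control. These address participants' expectations, not a rater who has learned the arm.
- *That a bias in CAPS points can be quoted.* The documents give neither the share of assisted participants nor the effect of unblinding on ratings. Any figure would also assume that forms precede the CAPS, that the helper is the rater, and that ratings shift in one direction.

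**Conclusion.** The concern holds as a gap in blinding procedure that should be closed. In assisted, paper or phone cases, the plan lets blinded staff handle a 4-month program evaluation and home-practice records that would reveal the arm. Nothing keeps these from the CAPS rater at the primary endpoint or before the 7-month CAPS.

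This rests on two assumptions: that open-ended answers and practice records identify the program, and that one person could both help with forms and conduct interviews. The first is very likely; the second is permitted but not stated. How many participants would be affected, and by how much ratings would move, cannot be derived from the documents. If nearly all forms are completed online and unaided, the effect would be small. The sample size and analysis model are not in question.

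**What to change.** Amend the assessment paragraphs of section 5.0 to state that:

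1. The CAPS is completed before any other form at the 4-month and 7-month visits.
2. Help with, receipt of and data entry for the program evaluation and home-practice records go to the project coordinator, who is already unblinded and assesses no outcomes, or the forms are self-completed online. They never go to the CAPS rater.
3. The CAPS rater does not conduct the HYP-only focus group.
4. Participants are asked not to name their program to the interviewer, and any unblinding is logged with its date and visit.

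Item 1 alone is not enough, because it does not protect the 7-month rating or guard against home-practice records seen earlier. Recording the rater's guess of arm is optional, since such guesses are hard to interpret once outcomes differ between arms.

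The cost is a minor reassignment of tasks among existing staff, a sentence in the interview script and a short log. No visit, measure or analysis changes.

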7.0 Study Withdrawal/Discontinuation

A participant may withdraw from the study at any time by notifying the PI, [name], of their request in writing. Additionally, participants may be urged to withdraw for clinical reasons, such as severe suicidal thoughts. Their participation may also be terminated at the discretion of the PI if they violate any rules or regulations of the Roudebush VA Medical Center.

8.0 Statistical Considerations

RELIEVE will involve a 2-arm, parallel group, RCT. Since participants cannot be blinded to treatment assignment, observed outcomes (if positive) could be affected by expectation bias. To account for this potential bias, we will assess treatment expectations at baseline and account for them in our analyses. We will

randomize at the patient level rather than the provider level for two reasons (1) randomization at patient level saves sample size; and (2) patients from the same provider in the two arms will be adjusted for “provider effect.” Contamination will also be low because there is relatively minimal involvement required of VA providers in RELIEVE. In addition, randomization will be stratified by veteran and non-veteran status and gender (4 strata) to avoid potential imbalance of these factors between the two arms. [name], PhD (statistician) will create a randomization scheme in REDCap for each of the four strata to randomize patients in blocks of 4 assignments within each of 4 stratum.

Sample size. Our sample size is calculated based on estimated differences of intervention effects between two arms on the primary outcome: CAPS total score at 4 months, or treatment end. The CAPS total score is a continuous measure (0-136) and reflects a combined score reflecting symptom frequency and symptom severity. A recently published yoga pilot study for patients with PTSD⁹ found a pre-treatment CAPS score of 77.33 (standard deviation = 28.6). Post-treatment scores were reduced by 34% (CAPS = 51.1, SD = 27.6, effect size = 0.9) from the yoga intervention. We powered on a medium effect size of 0.55 which requires a larger sample size than 0.9. We recognize the correlation of outcomes from subjects within the same yoga class may reduce the effective sample size compared to the same sample with independent observations. This possible “clustering effect” has implications for power. Randomization will occur at the individual not cluster or clinic level. Also, we expect that the intra-cluster correlation (ICC) will be near zero because groups will have a mixture of participants from the various recruitment sites: therefore, there is no reason to believe that participants within groups would be more correlated on the outcomes than participants from different groups. We have no preliminary data to estimate the intra-cluster correlation (ICC) for participants within the same group. However, based on similarly designed published studies, we expect the ICC to be relatively small and balanced across the two treatment arms since the cluster sizes will be similar. We will assume an ICC of 0.05 for both groups. We will also assume a 20% difference between treatment groups. The absolute score difference at 4 months is estimated to be approximately 15.4 points (61.6, 80% of 77). Assuming a common standard deviation of 28 and using a two-sample t-test, we will need 60 evaluable subjects in each arm to detect such a difference (Cohen’s $d = 0.55$) with >85% power and 5% Type I error rate. With approximately 8 subjects per treatment group/class session or cluster, the design effect is $1 + (8-1) \times 0.05 = 1.35$. Therefore, we will inflate our sample size by 35% to accommodate the potential clustering effects. We then need 81 evaluable subjects in each arm. With an assumed 30% attrition, we will then need $(81 \times 2) / 0.70 = 232$ subjects (116 in each arm).

Data analysis: Baseline characteristics of the RELIEVE sample. To evaluate representativeness, we will compare enrollees and those who decline enrollment on baseline characteristics (socio-demographic variables, psychiatric comorbidity, and current and prior PTSD treatments). Any differences will be considered when interpreting results of subsequent analyses. We will also examine differences in baseline characteristics between patients who remain in the study and those who dropout. The linear mixed modeling approach (see next section) will ensure that all available data are used for subjects who have missing data. The models will also incorporate dropout status to adjust for follow-up missing data pattern. All participants will have baseline data. The possible missing data patterns will be (1) missing 4 month, not 7 month, (2) missing 7 month, not 4 month, (3) missing both 4 and 7 months, and (4) complete data.

Main analysis of the primary outcome. Our main analysis will use the ANCOVA (analysis of covariance) approach to linear mixed modeling of repeated measures in which the baseline measure of the relevant outcome scores (i.e., CAPS or PCL) is adjusted as a covariate in the model.⁸⁵ The model for CAPS will be adjusted for baseline CAPS score. The model for PCL, a continuous measure with a possible range of 17-85, will be adjusted for baseline PCL score. The CAPS and PCL are measured at every time point (baseline, 8 weeks, 4 months, 7 months) except the CAPS is not administered at 6 weeks in order to reduce participant burden, since the CAPS and PCL are highly correlated. We plan an intent-to-treat analysis with the primary endpoint at 4 months and evaluation of “early” response at 8 weeks and “sustained” response at 7 months (3 months post-intervention). The models will simultaneously incorporate three post-baseline measures (8 weeks ([PCL only], 4 months, and 7 months) of the relevant response variable. The main predictors will be group (treatment arm), time (categorical with indicator variables to avoid restrictive assumption of linearity over time), and their interaction. A random intercept will be used to adjust for the potential clustering effect for patients in

a specific yoga group. And a subject-specific random intercept (nested within the group effect) will accommodate the correlation among repeated measurements from the same patient. Aim 1 will involve testing intervention effects by using the appropriate contrast from the model to test the difference in CAPS score and PCL score between the two treatment arms at 8 weeks (early response), 4 months (the primary end point which occurs immediately post intervention), and 7 months (sustained effect of intervention). Descriptive statistics including adjusted means, SD, and effect sizes (differences between two arms on adjusted means divided by pooled SD) will be reported for outcomes at each time point. Variables that are either known, or shown with our data, to be significantly correlated to the outcomes, will be considered as covariates, irrespective of their degree of baseline imbalance between randomized groups (e.g., combat vs. con-combat PTSD, baseline credibility score, and mTBI).

Secondary analysis of primary outcome. For the CAPS and PCL total scores, we will also report a clinically relevant descriptive statistic in which we define the patients with more than 30% reduction from baseline as “responders.” We will then compare the probability of responders between treatment arms using a generalized linear mixed model with a logit link. The responding status of each patient at 8 weeks (for PCL only), 4 months and 7 months will be used as the outcome variables. Main predictors are group (treatment arm), time (8 weeks for PCL only, 4 months and 7 months) and their interaction. A significant coefficient of group indicates a significant odds ratio of being a responder between the two arms.

Analysis of secondary outcomes. Since RELIEVE is not specifically powered for secondary outcomes, these results should be interpreted cautiously unless they are highly significant ($p < .001$). PTSD-specific symptoms (anger, sleep) and PTSD-related symptoms/outcomes (well-being/QOL, depression, anxiety, pain) will be analyzed using the linear mixed modeling approach described above for the primary outcome. The secondary outcomes will be PTSD-specific symptoms including: anger (STAXI score), sleep (MOS score) and PTSD-related symptoms/outcomes: depression (BDI score), anxiety (STAI score), well-being/QOL (SF-12), and pain (BPI). Since there will be a number of secondary outcomes, we will adjust for multiple-comparisons by using the false discovery rate (FDR)⁸⁶ method to control the overall false positive rate at 0.05. Exploratory analyses of potential mediators/moderators: interoceptive awareness and self-regulation. Moderation effects will be assessed by testing two-way interactions between intervention group membership and demographic and baseline scales including treatment credibility, interoceptive awareness, self-regulation and type of trauma (combat vs non-combat related), mTBI. Mediation effects will be analyzed using the MPLUS structural equation modeling (SEM) software to test the direct, indirect, and total effects of paths in a multilevel SEM model that includes potential mediators measured at various study points (see table of measures) including client satisfaction, interoceptive awareness and self-regulation. Adherence to the interventions and home practice will also be assessed for its dose-response effects on the primary and secondary outcomes.

Missing data.⁸⁷ Based on our prior studies, we anticipate a possible dropout rate of 30%, which is reflected in the sample size calculation. We will first run a logistic model with missing status as the response variable, intervention arm, patients’ demographic characteristics as covariates, to check whether the missing status depends on the intervention group assignment and patient characteristics. Second, our linear mixed effects model can accommodate missing-at-random (or MAR which is assumed in many trials) where no bias will be introduced by ignoring the missing-data mechanism. If drop-outs are Missing Not At Random (MNAR), meaning the likelihood of drop-out depends on an un-observed outcome, and the missing data mechanism is ignored, potential bias can be introduced. We will run sensitivity analyses using linear mixed models with the “multiple imputation” method and 100 generated data sets to compare results with the standard linear mixed effects modeling without imputation to assess the robustness of the inference.

